9.1.20 Blood Volume

Total blood sampling volume for subjects will approximately be 370 mL. Even in case of further unexpected blood sampling, extension of blood sampling period or necessary retesting, sampling volume will increase to approximately 400 mL.

10.0 ADVERSE EVENTS

10.1 Definitions

10.1.1 Adverse Event (AE)

An AE is any undesirable and unintended medical event occurring to a subject in a clinical study, whether or not related to the study products. This includes events from the first study related activity after the subject has signed the informed consent and until post treatment follow-up period as defined in the protocol. The following should not be recorded as AEs, if recorded as medical history/concomitant illness on the CRF at screening:

- Pre-planned procedure, unless the condition for which the procedure was planned has worsened from the first study related activity after the subject has signed the informed consent
- Pre-existing conditions found as a result of screening procedures
- Pre-existing events that has not worsened in intensity or frequency from baseline

10.1.2 Treatment Emergent Adverse Event (TEAE)

A treatment-emergent AE (TEAE) is defined as any clinically significant event not present before exposure to study drug or any event already present that worsens in either intensity or frequency after exposure to study drug.

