6.2 Study Description

Each subject will undergo the following procedures during the study:

Screening Visit:

Before the screening takes place, potential subjects for the trial will be provided with written and oral information about the trial and the procedures involved. Subjects must sign the informed consent form (ICF) prior to entering the study. Please see section 9.1.1 for further details.

The screening visit will be performed up to 28 days prior to the first dosing day, to identify eligible subjects for the study. All assessments performed at the screening visit are stated in Table 16-1 and will be recorded in the electronic case report form (eCRF). Please see section 9.1.2 and 11.2 for further details.

In-house Period:

Subjects will check in to the clinical research unit (CRU) in the morning of Day -2 for a 9-day in-house period. They will receive standardized meals throughout their in-house stay. A 12-lead standard ECG will be performed. Subjects will be connected to an ABPM system for measurement of blood pressure (BP), and measurements will be started overnight on Day -2 to familiarize the subjects with the device. Measurements will continue until the morning of Day 4.

In the morning of Day -1, subjects will get connected to a Holter ECG for continued measurement of the heart rate activity until the morning of Day 4.

Only 24-hour monitoring data from Day -1 to Day 1 will be used for the monitoring evaluation as baseline assessments for ABPM and Holter ECG monitoring. For measuring timepoints, please see sections 9.1.14 and 9.1.15.

Subjects will be randomized to a single SC injection of HM15211 or placebo. Randomization will take place as close to the drug administration as possible.

On Day 1, after an \geq 10 h overnight fast, subjects will be dosed with HM15211or placebo at approximately 08:00 hours (t=0), through SC injection into the abdominal wall by qualified study staff. Measurements of vital signs, ECG, blood sampling for PK and PD analyses, local injection site evaluation, and laboratory parameter will be performed for safety evaluation, at timepoints stated in Table 16-1.

ABPM and Holter ECG monitoring will be continued until the morning of Day 4 for the post-dose evaluation. 24-hour monitoring evaluations will be performed together with available PK data, in order to determine the best time period for 24-h monitoring period around PK_{peak}.

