10.4 Procedures

10.4.1 Collection and Recording of AEs

Collection of all AEs (serious AEs and non-serious AEs) will commence from the time the subject signs the informed consent to participate in the study until the post-treatment follow-up visit. Throughout the in-house treatment period, the Investigator will assess whether any subjective AEs have occurred. In order to avoid bias in eliciting AEs, a non-specific question, such as "How have you been feeling since your last visit?" may be asked. Subjects may report AEs occurring at any other time during the study.

All subjects experiencing AEs, whether considered associated with the use of the study medication or not, must be monitored and given appropriate medical treatment at the discretion and judgement of the Investigator until the symptoms subside and any clinically relevant changes in laboratory values have returned to baseline or until there is a satisfactory explanation for the changes observed. All AEs will be documented in the AE page of the CRF, whether or not the Investigator concludes that the event is related to the drug treatment. The event term, start and stop dates, severity, action taken with study drug and outcome, will be documented, along with the Investigator's opinion of the causal relationship between the event and the study drug.

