12.2.5 Safety Analysis and Endpoints

Safety and tolerability of the study drugs will be assessed by collection and review of adverse events, tolerability, laboratory parameters, physical examination, vital signs, and ECG parameters throughout the duration of the study. Immunogenicity of HM15211 will be assessed by the development of ADAbs, nAbs and anti-PEG.

Safety analysis will involve examination of the descriptive statistics and individual subject listings for any effects of study treatment on clinical tolerability and safety.

The 24-hour blood pressure (day and night time systolic/diastolic BP) collected from ABPM, and 24-hour Holter ECG (HR, HRV [eg, difference between day and night HR, NN intervals, SDNN]) will be summarized descriptively.

AEs will be summarized using the safety analysis set. Placebo patients will be pooled across cohorts in the safety analysis.

All AEs will be coded using MedDRA. Data will be summarized using preferred term and primary system organ class.

Adverse event summaries will include the overall incidence (by system organ class and preferred term), events by maximum intensity, event by relationship to study treatment,

events leading to discontinuation of study drug, and serious adverse events. Physical exam, vital signs, blood pressure assessed by ABPM, heart rate assessed by Holter ECG, 12-lead ECG data, and laboratory parameters (hematology, chemistry, and urinalysis) will be summarized descriptively by treatment.

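### The TEAE definition in Protocol 10.1.2 restricts new events to clinically significant ones, and the AE summaries in 12.2.5 do not say that they count only post-dose events

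*Protocol*

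**What the plan says.** Section 10.1.2 has two limbs. For new events, a TEAE "is defined as any clinically significant event not present before exposure to study drug". For existing events, it is "any event already present that worsens in either intensity or frequency after exposure to study drug". Only the first limb carries a significance condition.

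Section 10.1.1 defines the parent term without one: "An AE is any undesirable and unintended medical event occurring to a subject in a clinical study". On timing it adds: "This includes events from the first study related activity after the subject has signed the informed consent". Section 10.4.1 agrees that collection "will commence from the time the subject signs the informed consent to participate in the study until the post-treatment follow-up visit". Section 6.2 sets the possible pre-dose span: "The screening visit will be performed up to 28 days prior to the first dosing day".

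The incidence of adverse events is the first primary endpoint listed in 5.1. For the analysis, 12.2.5 states: "AEs will be summarized using the safety analysis set". It then lists summaries by system organ class and preferred term, maximum intensity, relationship, discontinuation and seriousness. Neither 12.2.5 nor the rest of section 12 mentions TEAEs.

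**The concern.** In a first-in-human single-dose study, the central safety table should count every adverse event that begins or worsens after the injection, and nothing else. The protocol's wording leads to neither count cleanly.

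A programmer who uses the protocol's TEAE definition applies a filter that the AE definition does not contain, and new post-dose events that nobody judged clinically significant drop out. Section 9.1.19 shows the conflict. It requires every irritation event to be recorded as an AE, on a scale whose first step above zero is barely perceptible erythema. Such a reaction can only arise after the injection, yet it is not a TEAE unless someone calls it clinically significant.

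A programmer who instead follows 12.2.5 literally tabulates AEs from consent onward. Events from the screening period, which the drug cannot have caused, then enter the incidence on both arms and dilute the active-placebo contrast.

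**Working it through.** The protocol states no AE rate, so there is no figure of its own to reproduce. The check compares the sections and then illustrates the size with assumed rates.

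**1. The threshold across sections**

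| Section | Event | Significance required? |
|---|---|---|
| 10.1.1 | any AE | no |
| 10.1.2, first limb | new after dosing | yes |
| 10.1.2, second limb | worsening after dosing | no |
| 9.1.19 | irritation at the injection site | no, all recorded as AEs |
| 10.4.1 | items documented per AE | none listed for significance |

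The items in 10.4.1 are term, start and stop dates, severity, action taken, outcome and causality. The protocol does ask for a significance judgement on laboratory results (9.1.8) and ECGs (9.1.11), but lists none for AEs in general. The filter therefore has no stated data source for most events.

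**2. Pre-dose share of the AE window**

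Inputs: up to 28 days before dosing (6.2), and follow-up on Day 30 ± 2 (6.2). Day 1 to Day 30 is 29 days.

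- Nominal: 28 / (28 + 29) = 28/57 = 49%.
- With the ± 2 days: 28/59 = 47% to 28/55 = 51%.

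These are maxima, because 28 days is the longest screening interval allowed.

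**3. Illustration: effect of counting from consent**

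Assumptions, none from the protocol: post-dose incidence 30% on placebo and 60% on active; pre-dose AE risk *b* equal on both arms and independent of post-dose events. Then

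mixed incidence = 1 − (1 − p)(1 − b), and the difference becomes (p_active − p_placebo)(1 − b).

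| b | Placebo | Active | Difference |
|---|---|---|---|
| 0 | 30% | 60% | 30 points |
| 5% | 1 − 0.70 × 0.95 = 33.5% | 1 − 0.40 × 0.95 = 62% | 28.5 points |
| 10% | 1 − 0.70 × 0.90 = 37% | 1 − 0.40 × 0.90 = 64% | 27 points |
| 20% | 1 − 0.70 × 0.80 = 44% | 1 − 0.40 × 0.80 = 68% | 24 points |

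The chance that at least one of 40 dosed subjects has a pre-dose AE is 1 − (1 − b)^40: 87% at 5%, 98.5% at 10% and nearly 100% at 20%. At these rates the question of what to count would very probably arise.

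**4. Illustration: effect of the significance filter**

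This cannot be sized from the protocol. If, by assumption, 25%, 50% or 75% of subjects with a post-dose AE had only new events not judged clinically significant, an incidence of 60% would be reported as 0.60 × 0.75 = 45%, 0.60 × 0.50 = 30% or 0.60 × 0.25 = 15%.

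**The case against.** The strongest reply is that the two harms exclude each other. If 12.2.5 does not use TEAEs, the filter affects no table planned in the protocol. If TEAEs are used, the pre-dose dilution disappears. That is correct, and the point is made here only as a choice between two unsatisfactory readings.

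Second, section 12.1 leaves the definition of analysis variables to the SAP, which was not available here, and restricting AE tables to treatment-emergent events is commonly done there. Section 12.2.5 nowhere says expressly that pre-dose AEs are counted; that follows only from applying the AE definition literally. This stands for the pre-dose half. It does not dispose of the definition, which is written in the protocol: an SAP that adopts it inherits the filter.

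Third, there are safeguards:
- The safety set holds dosed subjects only (12.2.1.1).
- Under 10.3, events without a plausible temporal sequence from dosing are classed as not related, so pre-dose events should stay out of the related-event rows.
- Subject listings are planned (12.2.5).
- Conditions found by screening procedures, and unworsened pre-existing events, are not AEs if recorded as history (10.1.1).
- Injection-site reaction is a primary endpoint in its own right (5.1), so local reactions would be reported whatever the TEAE wording.

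These limit the damage, but none of them supplies the overall incidence of post-dose AEs.

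A reader might also infer that the filter removes mild events. The protocol does not support that: severity is a separate scale (10.2), and a mild event may be judged clinically significant.

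**Conclusion.** The point holds as a defect of definition. The significance condition on new-onset TEAEs conflicts with the AE definition, is not applied to worsening events, and has no listed data item behind it. Any table using it would undercount post-dose events. Separately, the literal wording of 12.2.5 admits pre-dose events in dosed subjects unless the SAP excludes them.

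A reader might go further and infer that no usable treatment-emergent count can be obtained. The documents do not support that: AE start dates (10.4.1) and actual dosing times (8.4) are recorded, so emergence by timing can be derived.

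A reader might also infer a severe loss of contrast. With an assumed constant background of 1.0 AE per subject per 30 days and a full 28 pre-dose days for everyone, the difference would shrink to exp(−28/30) = 39% of its size. The protocol gives no rate to justify that, and 28 days is the maximum. Under the assumed pre-dose risks of 5% to 20%, 95% to 80% of the difference remains. The direction (dilution) is clear under equal and independent pre-dose risks; the size is not known. The study is descriptive and tests no hypothesis (6.3), so what is affected is the reported incidence and its comparison with pooled placebo, not a formal test.

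**What to change.** - **Section 10.1.2:** delete the words *clinically significant* and define a TEAE as any AE with onset, or worsening in intensity or frequency, after dosing and through the follow-up visit.
- **Section 12.2.5:** state that the AE summary tables count TEAEs so defined, and that AEs with onset before dosing, without later worsening, are listed separately.
- **SAP:** use the same definition, with a convention for events that start on Day 1 when only the date is known.

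The cost is one edited sentence and one added sentence in the protocol, plus matching SAP text. No new data are needed and no study procedure changes.

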10.1.3 Clinical Laboratory Event

A clinical laboratory AE is any clinically significant laboratory abnormality that suggests a disease and/or organ toxicity and is of a severity, which requires active management, (i.e. change of dose, discontinuation of study product, more frequent follow-up, or diagnostic investigation).

A laboratory re-test and/or continued monitoring of an abnormal value is not considered an intervention. In addition, repeated or additional noninvasive testing for verification, evaluation or monitoring of an abnormality is not considered an intervention.

10.1.4 Adverse Reaction

An adverse reaction is defined as any adverse event caused by a drug. Adverse reactions are a subset of all suspected adverse reactions where there is reason to conclude that the drug caused the event.

10.1.5 Suspected Adverse Reaction

Suspected adverse reaction is defined as a subset of any adverse event for which there is a reasonable possibility that the drug caused the adverse event. For the purposes of IND safety reporting, 'reasonable possibility' means there is evidence to suggest a causal

relationship between the drug and the adverse event. A suspected adverse reaction implies a lower degree of certainty about causality than adverse reaction, which means any adverse event caused by a drug.

Reasonable possibility is given if:

- A single occurrence of an event that is uncommon and known to be strongly associated with drug exposure
- One or more occurrences of an event, that is not commonly associated with drug exposure, but otherwise uncommon in the population exposed to the drug
- An aggregate analysis of specific events observed in a clinical study that indicates those events occur more frequently in the drug treatment group than in a concurrent or historical control group.

10.1.6 Unexpected Adverse Event/ Unexpected Suspected Adverse Reaction

An unexpected AE/unexpected suspected adverse reaction is an AE or suspected adverse reaction that is not listed in the Investigator Brochure or Protocol, as occurring with a class of drugs or as anticipated from the pharmacological properties of the drug, but are not specifically mentioned as occurring with the particular drug under investigation, or is not listed at the specificity or severity that has been observed; or, if an Investigator Brochure is not required or available, is not consistent with the risk information described in the general investigational plan or elsewhere in the current application.

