HM15211 is a long-acting GLP-1/Glucagon/GIP triple agonist with extended half-life through reduced renal clearance and possibly by vascular endothelial recycling via FcRn binding. HM15211 showed triple-agonistic properties with potent glucagon activity in addition to balanced GLP-1 and GIP activity.

According to series of in vivo pharmacologic studies, HM15211 can be an attractive treatment option for obese patients based on its potent body weight loss efficacy from

energy intake inhibition and energy expenditure enhancement. Glucagon activity provides potent body weight loss primarily from fat mass reduction as shown in efficacy studies in diet-induced obesity (DIO) mice. Furthermore, GLP-1/GIP activities negate a possible hyperglycemic risk as demonstrated in intra-peritoneal glucose tolerance test (ipGTT) studies in normal and DIO mice.

Above all, liver preferential distribution, and following hepatic lipid metabolism improvement, renders HM15211 a suitable therapeutic option for NASH and hepatic fibrosis. Therefore, HM15211 is expected to have favorable therapeutic profiles in both, obesity and NASH as well as convenience in its clinical dosing regimen.

For further information please refer to the Investigator's brochure (IB).

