4.3 Summary of Pre-Clinical Studies

To date, no human studies have been conducted with HM15211.

In vitro activity of HM15211 was evaluated using respective receptors, human GLP-1 receptor (hGLP-1R), human glucagon receptor (hGlucagonR), and human GIP receptor (hGIPR). HM15211 showed dose-dependent activation of all three receptors with potent glucagon activity in addition to balanced GLP-1 and GIP activity. Simultaneous activation of three incretin receptors could provide synergistic metabolic benefits on body weight loss and lipid profile improvement whilst avoiding hyperglycemic risk.

Further in vitro studies confirmed, that since HM15211 includes an aglycosylated Fc moiety derived from human IgG4, it shows minimal immune-mediated effector functions. In addition, due to Fc moiety, HM15211 retained pH-dependent FcRn binding property, which is essential for vascular endothelial recycling.

In vivo pharmacology studies using obese mice showed that HM15211 enables potent body weight loss from both, food intake inhibition and enhanced energy expenditure. The body weight loss was mainly from fat mass reduction, along with lowered serum lipid profile. Glucagon action increased energy expenditure and thus enhanced body weight loss and hyperglycemic risk by glucagon was effectively buffered by actions of GLP-1/GIP. In NASH induced models, HM15211 effectively reduced hepatic triglycerides

(TG), oxidative stress and inflammatory markers. Furthermore, HM15211 treated animals showed significant reduction in NAFLD activity score and hepatic fibrogenic markers, suggesting HM15211 as an effective pharmacotherapy for NASH with hepatic fibrosis.

Safety pharmacology studies were conducted to evaluate the effects on the cardiovascular, respiratory, central nervous systems and in vitro hERG channel assay. No significant effect was observed in the safety pharmacology studies and in vitro human ether-a go-go related gene (hERG) channel assay.

In pharmacokinetic studies, HM15211 exhibited a prolonged half-life (t½) after subcutaneous (SC) or intravenous (IV) dosing, which ranged from approximately 42.7 to 85.6 hours in mice, 74.7 to 86.0 hours in rats, and 35.7 to 79.7 hours in dogs, indicating that HM15211 is a long acting triple-agonist. HM15211 is preferentially distributed in the liver, making HM15211 a favorable treatment option for dysfunction in lipid metabolism specifically in the liver.

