10.3 Relationship to Study Treatment

The relationship of each AE to the study drug(s) will be assessed by the Investigator or Sub-Investigator on the basis of his/her clinical judgment and the following definitions:

1= Related:

The AE follows a reasonable temporal sequence from the study product administration, and cannot be reasonably explained by the subject's clinical state or other factors (e.g., disease under study, concurrent diseases, or concomitant medications).

The AE follows a reasonable temporal sequence from the investigational product administration, and represents a known reaction to the drug under study or other drugs in its class, or is predicted by the known pharmacological properties of the drug.

The AE resolves with discontinuation of the investigational product and/or recurs with rechallenge, if applicable.

2 = Not Related:

The AE does not follow a reasonable temporal sequence from investigational product administration, or can be reasonably explained by the subject's clinical state or other factors (e.g., disease under study, concurrent diseases, and concomitant medications).

3= Not Assessable/ Not Classifiable:

The AE cannot be judged because of insufficient or contradictory information. The AE cannot be supplemented or verified.

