10.6.1 Safety Reporting to IRBs or IECs, and Regulatory Authorities

The Sponsor or designated qualified vendor will be responsible for reporting all suspected unexpected serious adverse reactions (SUSARs) and any other applicable SAEs to regulatory authorities, Investigators, and IRBs or IECs, as applicable, in accordance with national regulations in the countries where the study is conducted.

Relative to the first awareness of the event by/or further provision to the Sponsor or Sponsor's designee, SUSARs will be submitted within 7 days for fatal and life-

threatening events and 15 days for other SUSARs, unless otherwise required by national regulations.

The Sponsor or designated qualified vendor will also prepare an expedited report for other safety issues where these might materially alter the current benefit-risk assessment of an investigational product or that would be sufficient to consider changes in the investigational product administration or in the overall conduct of the study. The investigational site will forward a copy of all expedited reports to his or her IRB or IEC in accordance with national regulations.

Reporting responsibilities of Investigator under 21 CFR 312.64(b) and Sponsor under 21 CFR 312.32(c)(1)(i) for serious and unexpected suspected adverse reactions will be followed.

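### Section 10.1.6 defines an unexpected reaction in a sentence that contradicts itself, so a reaction listed only as a class or pharmacological effect can be classed as expected

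*Protocol*

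**What the plan says.** Protocol Section 10.1.6 defines an unexpected adverse event or unexpected suspected adverse reaction in one long sentence. Its parts are:

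- an opening condition: the event is one "that is not listed in the Investigator Brochure or Protocol, as occurring with a class of drugs or as anticipated from the pharmacological properties";
- a closing clause attached to it: "but are not specifically mentioned as occurring with the particular drug under investigation";
- a second route: "or is not listed at the specificity or severity that has been observed";
- a third route, which applies only "if an Investigator Brochure is not required or available" and compares the event with the risk information given elsewhere.

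Two duties use the term. Under Section 10.6.1 the sponsor or its vendor "will be responsible for reporting all suspected unexpected serious adverse reactions (SUSARs) and any other applicable SAEs", with 7 days for fatal and life-threatening events and 15 days for other SUSARs. Under Section 14.1 the investigator must promptly tell the IEC/IRB of unexpected SAEs with a possible causal link.

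Section 4.3 gives the setting: "To date, no human studies have been conducted with HM15211".

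**The concern.** The opening condition and the closing clause pull in opposite directions. The opening makes an event unexpected when it is not listed as a class or pharmacological effect. The closing clause is a contrast: it picks out events that are mentioned in that way but not for this particular drug. It has nothing to contrast with unless the events are mentioned for the class or the pharmacology. The change of verb from singular to plural between the two parts also suggests that the words opening a second condition were lost.

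At stake is onward reporting. Section 10.3 counts it towards a judgement of related when an event "represents a known reaction to the drug under study or other drugs in its class". Section 10.1.6, taken literally, lets the same class knowledge make the event expected. A serious event could therefore be judged related because the class is known to cause it, and fall outside the SUSAR definition for the same reason. In a first-in-human trial, what can be foreseen for humans comes largely from pharmacology, class knowledge and animal data, so this is a category worth defining correctly.

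**Working it through.** No arithmetic applies and the Protocol gives no figure to reproduce. The check is to read the sentence as a logical rule and apply it to each kind of event.

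**Inputs**
- The opening condition, closing clause and specificity/severity route, all from Section 10.1.6.
- The no-brochure route from Section 10.1.6. It does not apply here, because Section 4.1 refers the reader to an Investigator's Brochure.

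**Readings of the opening condition with its closing clause**
- Reading A: the negation governs the class phrase. Unexpected = not listed for class or pharmacology, and not mentioned for HM15211.
- Reading B: the class phrase is left dangling. Unexpected = not listed in the brochure or Protocol at all.
- Apparent intent, from the closing clause: unexpected = not listed at all, or mentioned for class or pharmacology but not for HM15211.

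The specificity/severity route is available under all three.

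| Event | Reading A | Reading B | Apparent intent |
|---|---|---|---|
| 1. Not listed anywhere | unexpected | unexpected | unexpected |
| 2. Listed for class or pharmacology only, in a milder or less specific form than observed | unexpected (second route) | unexpected (second route) | unexpected |
| 3. Listed for class or pharmacology only, at the observed specificity and severity | **not unexpected** | **not unexpected** | **unexpected** |
| 4. Mentioned for HM15211 at the observed specificity and severity | not unexpected | not unexpected | not unexpected |

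The readings part company on row 3 only. There, both literal readings give the opposite of what the closing clause was written to achieve.

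**Tracing row 3 forward**
- Section 10.4.2: the site still reports the event to the sponsor within 24 hours, because all SAEs go forward whatever their judged causality. Nothing is lost at this step.
- Section 10.6.1: the 7- or 15-day submission depends on the event being unexpected. This step is exposed.
- Section 14.1: the investigator's prompt report to the IEC/IRB also depends on the event being unexpected, and that sentence cites no regulation that would supply another definition. This step is exposed too.
- Sections 6.4.1 and 12.2.5: neither the dose-escalation stopping criteria nor the adverse-event summaries use expectedness. Nothing changes there.

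**The case against.** **The regulation governs in any case.** Section 10.4.2 says that reporting of serious and unexpected events will follow 21 CFR 312.32. Section 10.6.1 repeats the commitment for investigator and sponsor, and Section 10.1.8 ties expedited evaluation to the same rule. Section 10.6.1 also covers other applicable SAEs, and requires an expedited report for safety issues that could change the benefit-risk balance. This stands as a real backstop on the sponsor's side. It is partial, because none of these sections says that the regulation overrides Section 10.1.6, and Section 14.1 does not cite it at the point where the investigator needs the definition.

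**The specificity/severity route catches the difficult cases.** It catches row 2. It does not catch row 3, which is the case the closing clause addresses.

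**This is a drafting slip with visible intent.** That is accepted. A reader might infer that the Protocol deliberately inverts the rule so that class effects count as expected. The text does not support this: its own closing clause points the other way, and the sentence has no single coherent literal meaning.

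**The size is unknown.** This also stands. A reader might infer that the serious reactions most plausible for this triple agonist would all escape expedited reporting, or that, with no human data, every class-listed serious reaction must be unexpected. Neither follows. The brochure is not shown, so it is not known which events it lists or in what terms. Section 10.5 lists only blood-draw risks. The closing clause asks whether an event is mentioned for HM15211, not whether it has been seen in humans, and Section 4.3 reports animal findings with HM15211 itself.

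**Conclusion.** Section 10.1.6 is garbled and self-contradictory, and should be corrected. Its defect is confined to one kind of event: a serious suspected reaction listed only for the class or the pharmacology, not mentioned for HM15211, and matching the listing in specificity and severity. Such an event can be classed as expected under either literal reading, although the sentence's own closing clause shows that it was meant to be unexpected.

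The consequence is a risk to expedited reporting under Section 10.6.1 and to IEC/IRB reporting under Section 14.1. It is not a certainty of missed reports, given the backstops above. The number of events affected cannot be stated without the Investigator's Brochure, and could be zero. No endpoint, analysis set, sample size or escalation rule is touched.

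The conclusion rests on the wording of Section 10.1.6 alone. It assumes that whoever judges expectedness works from that definition and does not go directly to the regulation.

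**What to change.** Reword Section 10.1.6 so that an event is unexpected if **any one** of the following holds:

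- (a) it is not listed in the Investigator's Brochure or Protocol, or is not listed there at the specificity or severity observed; **or**
- (b) it is mentioned there only for the drug class or as an effect anticipated from pharmacology, and not specifically for HM15211; **or**
- (c) where no Investigator's Brochure is required or available, it is inconsistent with the risk information in the investigational plan or elsewhere in the application.

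State explicitly that the three are alternatives, so that the list cannot be read as requiring more than one. Keep (c), which is already in the present sentence. Carry the same wording into any safety-reporting plan that uses the term.

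The cost is one reworded definition and possibly a few additional expedited reports. No data collection, analysis or timeline changes.
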